9.1 Discontinuation

9.1.1 Discontinuation of study treatment

Discontinuation of study treatment for a subject occurs when study treatment is stopped earlier than the protocol planned duration, and can be initiated by either the subject or the investigator.

The investigator must discontinue study treatment for a given subject if, he/she believes that continuation would negatively impact the subject's well-being.

Study treatment must be discontinued under the following circumstances:

- Subject/guardian decision
- Pregnancy
- Use of prohibited treatment as per recommendations in the prohibited treatment section

- Any situation in which study participation might result in a safety risk to the subject

In addition during the Extension Phase, study treatment should be discontinued under the following circumstances

- Patient is no longer clinically benefitting from treatment in the opinion of the investigator
[REDACTED]

If discontinuation of study treatment occurs, the investigator should make a reasonable effort to understand the primary reason for the subject's premature discontinuation of study treatment and record this information.

Subjects who discontinue study treatment or who decide they do not wish to participate in the study further should NOT be considered withdrawn from the study UNLESS they withdraw their consent (see withdraw of informed consent section.). **Where possible, they should return for the assessments indicated** in the assessment schedule. If they fail to return for these assessments for unknown reasons, every effort (e.g. telephone, e-mail, letter) should be made to contact the subject/pre-designated contact as specified in the lost to follow-up section. This contact should preferably be done according to the study visit schedule.

If the subject cannot or is unwilling to attend any visit(s), the site staff should maintain regular telephone contact with the subject, or with a person pre-designated by the subject. This telephone contact should preferably be done according to the study visit schedule.

After study treatment discontinuation, at a minimum, in abbreviated visits, the following data should be collected at site visits or via telephone/email contact:

- new / concomitant treatments
- adverse events/Serious Adverse Events

The investigator must also contact the IRT to register the subject's discontinuation from study treatment.

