5. action taken regarding with study treatment All adverse events must be treated appropriately. Treatment may include one or more of the following:
 - Dose not changed
 - Dose Reduced/increased
 - Drug interrupted/withdrawn
6. its outcome
 - a. not recovered/not resolved;
 - b. recovered/resolved;
 - c. recovered/resolved with sequelae;
 - d. fatal; or unknown.

Conditions that were already present at the time of informed consent should be recorded in medical history of the subject. Adverse events (including lab abnormalities that constitute AEs) should be described using a diagnosis whenever possible, rather than individual underlying signs and symptoms. Adverse event monitoring should be continued for at least 30 days following the last dose of study treatment.

Once an adverse event is detected, it must be followed until its resolution or until it is judged to be permanent (e.g. Continuing at the end of the study), and assessment must be made at each visit (or more frequently, if necessary) of any changes in severity, the suspected relationship to the interventions required to treat it, and the outcome.

Information about adverse drug reactions for the investigational drug can be found in the prescribing information/package insert/CDS.

Abnormal laboratory values or test results constitute adverse events only if they fulfill at least one of the following criteria:

- they induce clinical signs or symptoms
- they are considered clinically significant
- they require therapy

Clinically significant abnormal laboratory values or test results must be identified through a review of values outside of normal ranges/clinically notable ranges, significant changes from baseline or the previous visit, or values which are considered to be non-typical in subjects with the underlying disease. Alert ranges for laboratory and other test abnormalities are included in [Section 16.1](#).

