Core phase	Treatment start date	
 1. Subject completes 52 weeks on core phase treatment i.e. if trt disposition reason is “COMPLETED” on DS domain 
 a. If subject does not enter PTA phase then use week 52 visit date b. If subject enters PTA phase then 
 i. Subject enters PTA on week 52 visit date then use a day prior to week 52 visit date ii. Subject enters PTA phase after week 52 then use week 52 visit date 2. Subject completes 52 weeks on core phase but discontinues treatment early i.e. core phase treatment disposition reason is not equal to “COMPLETED” on DS domain 
 a. If subject does not enter PTA phase 
 i. if week 52 visit date > treatment end date plus 27/1 day then use treatment end date plus 27/1 day ii. if week 52 visit date <= treatment end date plus 27/1 day then use week 52 visit date b. If subject enters PTA phase 
 i. if week 52 visit date > treatment end date plus 27/1 day then use treatment end date plus 27/1 day ii. if week 52 visit date <= treatment end date plus 27/1 day then use a day prior to first dose in PTA phase 3. Subject discontinues treatment early and does not complete 52 weeks on core phase i.e. core phase trt disposition reason is not equal to “COMPLETED” on DS domain and Week 52 visit date is not available in SV domain and study disposition reason is equal not to “COMPLETED” on DS domain 
 a. If treatment disposition date > treatment end date plus 27/1 day then use treatment end date plus 27/1 day b. If treatment disposition date <= treatment end date plus 27/1 day then use treatment disposition date
Safety follow up	Core phase end plus 1 day	
 a) If subject does not enter PTA phase then use study disposition date; b) If subject enters PTA phase then use a day prior to first dose in PTA phase
PTA phase	First erenumab injection	
 1. If subject completes 52 weeks on PTA phase then use min (trt disposition or study disposition date)

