	date in PTA phase	
2. If subject discontinues prior to completing 52 weeks on treatment in PTA phase i.e. treatment disposition reason is not equal to “COMPLETED” on DS domain then
 
 If treatment disposition date > treatment end date plus 27 day then use trt end date plus 27 day If treatment disposition date <= treatment end date plus 27 day then use trt disposition date
--	-------------------	--

	Start time point	End time point
Initially assigned treatment (IAT) period (core phase)	Treatment start date	
1. Subject completes 52 weeks on IAT i.e. core phase treatment disposition reason is “COMPLETED” and week 52 visit date is non-missing in SV domain and date of switching is missing on DS domain
 
 If subject does not enter PTA phase then use week 52 visit date from SV domain If subject enters PTA phase then 
 i. Subject enters PTA on week 52 visit date then use a day prior to week 52 visit date ii. Subject enters PTA phase after week 52 then use week 52 visit date 
2. Subject completes 52 weeks on core phase but permanently discontinues IAT early i.e. trt disposition reason is not equal to “COMPLETED” on DS domain and week 52 visit date is non-missing in SV domain and date of switching is missing on DS domain
 
 If subject does not enter PTA phase 
 i. if week 52 visit date > treatment end date plus 27/1 day then use treatment end date plus 27/1 day ii. if week 52 visit date <= treatment end date plus 27/1 day then use week 52 visit date If subject enters PTA phase 
 i. if week 52 visit date > treatment end date plus 27/1 day then use treatment end date plus 27/1 day

		
 ii. if week 52 visit date \leq treatment end date plus 27/1 day then use a day prior to first dose in PTA phase 3. Subject does not complete 52 weeks on study and permanently discontinues IAT i.e. week 52 visit date is missing in SV domain and date of switching is missing on DS domain and core phase treatment disposition reason is not equal to "COMPLETED in DS domain then use min(trt disposition date, trt end date plus 27/1 day) 4. Subject switches IAT then use day prior to date of first switch on DS domain

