2.3.1 Subject disposition

Subject disposition will be summarized on FAS. The number and percentage (based on the number of subjects within each randomized treatment arm) of subjects who completed / discontinued the study will be displayed by initially assigned treatment and overall. The primary reason for premature study discontinuation will be displayed by initially assigned treatment and overall. The core phase completers are defined as subjects who either complete week 52 on study or complete safety follow up visit.

Treatment completion will be summarized in the same manner as subject disposition. The number and proportion of subjects, who complete the study treatment or discontinue the study treatment prematurely along with the primary reason for study drug discontinuation will be presented.

Disposition and treatment completion data will also be presented in listings.

Screen Failures: The total number of subjects screened and the number of subjects screened, but not randomized (discontinued prior to screening or baseline phase completion) will be summarized, including the reason for screening failure. Data on screen failures will also be presented in listings.

Analysis sets: The number of subjects within each of the analysis sets used in the study will be summarized.

The impact of COVID-19 pandemic on study subjects with respect to randomization, study and treatment discontinuations, protocol deviations and dose interruptions will be assessed and summarized for pre- and during COVID-19 phases. The pandemic phase will be defined based on start date of pandemic. For Italy start date of pandemic will be used as 23Feb2020 and for rest of the world start date of pandemic will be used as 01March2020.

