5.6 Important derivations

- Subject-level End of Study (EOS) Date

The end of study (EOS) date for each subject is defined as the last date on which the subject participated in the study. The date will be recorded on the study disposition eCRF page.

- Duration of exposure of study treatment

For AMG334 calculation of exposure, dose date refers to receiving dose > 0 , but can include partial doses. The duration of exposure for AMG334 is computed as of last injection of study drug + 27 days - date of first injection of study drug +1.

For oral prophylactics arm calculation of exposure, dose date refers to receiving dose > 0 . The duration of exposure for initially assigned treatment is computed as last dose date - First Dose Date + 1.

- Compliance with the eDiary

The protocol requirement is 80% compliance in 28 days. That means a minimum 23 diaries must be completed within 28 days. Compliance to eDiary at each month is calculated as

- (Number of eDiary entered in baseline period or between IP doses/28days)*100% if the number of actual days in Baseline period or between IP doses interval is ≤ 28 days
 - (Number of eDiary entered in baseline period or between IP doses/ number of actual days in Baseline period or between IP doses interval)*100% if the number of actual days in Baseline period or between IP doses interval is > 28 days
 - eDiary Device Assignment Date

The date on which an eDiary device is assigned to a subject for the first time after completion of initial screening at week -4 visit.
 - eDiary Day

A day in which a subject uses the eDiary.
 - Information Day

A day which is either a headache day or an eDiary day.
 - Migraine Day

A migraine day is defined as any calendar day in which the subject experiences a qualified migraine headache (onset, continuation, or recurrence of the migraine headache). Please see exceptions in [Appendix 5.7](#). A qualified migraine headache ([IHS, 2013](#)) is defined as a migraine with or without aura, lasting for ≥ 30 minutes, and meeting at least one of the following criteria:

 1. ≥ 2 of the following pain features:
 - Unilateral
 - Throbbing
 - Moderate to severe
 - Exacerbated with exercise/physical activity
 2. ≥ 1 of the following associated symptoms:
 - Nausea and/or vomiting
 - Photophobia and phonophobia

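### For early stoppers, SAP Table 2-2 puts the same observed post-dose days in the treatment interval or in safety follow-up, depending on later Week 52 attendance

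*SAP*

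**What the plan says.** SAP 2.1.1.6, Table 2-2, defines the Core phase and initially assigned treatment (IAT) intervals for safety by disposition scenario.

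- **Item 2** (treatment stopped early, Week 52 visit present): "if week 52 visit date > treatment end date plus 27/1 day then use treatment end date plus 27/1 day". If the Week 52 visit comes sooner, that visit or the start of post-trial access sets the end. The treatment disposition date plays no part.
- **IAT item 3** (treatment stopped early, no switch, no Week 52 visit): "then use min(trt disposition date, trt end date plus 27/1 day", closing the bracket.
- **Core item 3b** has the same effect: "If treatment disposition date <= treatment end date plus 27/1 day then use treatment disposition date". Core item 3 further requires that study disposition is not coded as completed; IAT item 3 does not.
- **Safety follow up** starts the day after core phase end and, without post-trial access, runs to the study disposition date. SAP 2.1.1.6 reports it under its own label.

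Protocol 9.1.1 says that subjects who stop treatment, or "who decide they do not wish to participate in the study further should NOT be considered withdrawn from the study", with withdrawal of consent as the exception. Protocol 10.1.1 adds: "Adverse event monitoring should be continued for at least 30 days following the last dose of study treatment". SAP 2.3.1 states: "The core phase completers are defined as subjects who either complete week 52 on study or complete safety follow up visit".

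**The concern.** Items 2 and 3 describe people in the same position on the day they stop. What separates them is whether a Week 52 visit takes place, possibly months later. The interval that holds an adverse event shortly after the last dose should not depend on attendance after that event, and the SAP gives no reason for it. The cap is also tied to the wrong date: the end of treatment does not end observation, so the rule can remove days on which the subject was still being followed.

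At stake is the content of any on-treatment safety summary built on these intervals. SAP 2.8.1 plans treatment-emergent tables and exposure-adjusted incidence rates. Because the add-on is 27 days for erenumab and 1 day for oral drugs, the cap can act on the two arms to very different extents.

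**Working it through.** **Inputs.** The interval rules and the 27/1-day add-on are from SAP Table 2-2, the exposure formulas from SAP 5.6, and the dosing window of 23 to 33 days from protocol 6.7.2 and section 8. Table 2-2 defines neither 27/1 nor treatment end date. I read them as erenumab/oral and as the date of last administration in SAP 2.1.1.2.

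**Check of that reading.** Erenumab exposure is "computed as of last injection of study drug + 27 days - date of first injection of study drug +1". For a single injection this is 0 + 27 − 0 + 1 = 28 days, the same as an interval from day 0 to day 27 inclusive. Oral exposure is "computed as last dose date - First Dose Date + 1", with no tail. Item 3 of the Switched row, where only oral drugs occur, uses plus 1 day. All three fit the reading.

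**Days removed.** Let day 0 be the last dose, d the treatment disposition day, s the study disposition day, and w the add-on (27 or 1). With a Week 52 visit after day w, item 2 ends at w. Item 3 ends at min(d, w). The difference is w − min(d, w).

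| d | Erenumab end, item 3 | Erenumab days removed | Oral days removed |
|---|---|---|---|
| 0 | 0 | 27 | 1 |
| 7 | 7 | 20 | 0 |
| 14 | 14 | 13 | 0 |
| 23 | 23 | 4 | 0 |
| 27 or later | 27 | 0 | 0 |

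A stop recorded at the next dosing visit (d from 23 to 33) therefore removes 4 down to 0 erenumab days.

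**Where the days go.** Safety follow-up covers day min(d, w) + 1 to day s. For erenumab with d = 0:

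- s of 27 or more: all 27 days are in follow-up.
- s = 10: 10 days are in follow-up and 17 fall after study exit.
- s = 0: all 27 fall after study exit.

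**Example.** Two erenumab subjects have the same last injection (day 0), treatment disposition on day 10 and an adverse event on day 20. One later attends Week 52: the interval ends on day 27 and the event is inside it. The other leaves on day 60 without a Week 52 visit: the interval ends at min(10, 27) = day 10 and the event falls in follow-up. Capped at study disposition, the second interval ends at min(60, 27) = day 27, and the two agree.

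**Exposure.** If the second subject had only one injection, SAP 5.6 counts 28 days of exposure while the interval holds 11 (day 0 to day 10). With d = 0 it holds 1. For a single oral dose, exposure is 1 day and the interval is 1 or 2 days, so this mismatch does not arise.

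**Core item 3 condition.** SAP 1.1 describes a follow-up visit under the earlier protocol versions, and SAP 2.3.1 counts those who complete it as completers. If such a subject stopped treatment early, has no Week 52 visit and is coded as completed, Core item 3 excludes them, and Core item 2 needs a Week 52 date that does not exist. The core phase end is then undefined, and with it the start of follow-up.

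**The case against.** The strongest reply is that nothing disappears. A reader might infer that up to 27 days of erenumab safety data are lost. The documents do not support that: days between treatment and study disposition go to safety follow-up, which is summarized, and SAP 2.8.1 lists all adverse events. Days after study exit are unobserved under any rule.

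A reader might also infer that erenumab harms are biased downward. That is not shown. SAP 2.8.1 does not tie treatment-emergent tables to these intervals. The only explicit on-treatment definition, in protocol 12.5.2, runs to 112 days after the last dose in both arms with no disposition cap, and SAP section 4 declares no change. Under that definition the day-20 event counts either way. An event that causes the stop normally precedes the disposition date and stays inside the interval. For the same delay d, the capped erenumab interval is never shorter than the oral one, since min(d, 27) is at least min(d, 1).

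The affected group may also be small. Treatment status is reviewed at 4-weekly visits, switchers fall under item 4 of the IAT row, and subjects wanting post-trial access must attend through Week 52. Table 8-1 gives Early Exit and Week 52 one column; if an early exit is stored as Week 52, item 2 applies. The documents do not settle this.

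These points limit the size of the problem but do not remove it. Stops need not wait for a visit: protocol 9.1.1 lets subject or investigator initiate them, and Appendix 2 lists liver findings with immediate discontinuation. Whatever add-on is adopted, a treatment-disposition cap in item 3 and none in item 2 leaves classification dependent on later attendance.

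**Conclusion.** The inconsistency stands. For early stoppers who do not switch, Table 2-2 moves observed days out of the treatment interval when no Week 52 visit follows: at most 27 days for erenumab and 1 day for oral drugs, and 0 to 4 erenumab days if the stop is recorded at the next dosing visit. This assumes that 27/1 means erenumab/oral and that treatment end date is the last dose date.

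The number of subjects and the effect on event rates cannot be derived. It is tempting to start from the protocol's one-year erenumab retention of 75–80% (394 × 0.20 = 78.8 to 394 × 0.25 = 98.5 subjects off drug) and multiply by an average loss. That needs the share who then miss Week 52 without switching, their disposition dates and their study exit dates. The documents give none of these, and an even spread of stops over the dosing interval does not fit 4-weekly review.

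Undercounting of erenumab events relative to exposure is conditional: it follows only if treatment-emergent tables or exposure-adjusted rates use these intervals with the uncapped exposure of SAP 5.6.

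The gap in Core item 3 matters only if a subject without a Week 52 visit is coded as completed. Protocol 9.2 ties Core completion to the Week 52 visit, so this may be rare or absent.

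**What to change.** In Table 2-2:

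1. Core item 3 and IAT item 3: end the interval at min(study disposition date, treatment end date + 27/1 day).
2. Switched item 3: end it at min(study disposition date, treatment end date + 1 day).
3. Core item 3: delete the condition that study disposition is not completed, so that every early stopper without a Week 52 visit gets an end date, as IAT item 3 already allows.

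Items 2 and 3 then apply one window, cut only where observation ends. A footnote should define 27/1 and treatment end date. The cost is SAP wording and a small change to the derivation program, with no new data; some events may move from follow-up to the treatment interval.

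Separately, reconcile the add-on with protocol 12.5.2. Against 112 days it is shorter by 112 − 27 = 85 days for erenumab and 112 − 1 = 111 days for oral drugs. The SAP should state which interval defines treatment-emergent events and record any departure in section 4.

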- Treatment discontinuation does not imply study discontinuation. Every effort should be attempted to ensure subjects complete the study visits event if treatment is discontinued. After study completion, post-trial access to AMG334 will be offered to the study participants as needed.
- Some eligibility criteria will be checked at screening visit and some at baseline.
- Treatment disposition form will be filled for the last drug taken by the subject regardless of switching and not only for initially assigned treatment.

[figure not shown]
- There can be gap between end of first treatment and start of switched treatment.

[figure not shown]

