Switched treatment period (core phase)	Date of first switch on DS domain	
 1. Subject completes 52 weeks on switched treatment i.e. core phase treatment disposition reason is "COMPLETED" and week 52 visit date is non-missing in SV domain 
 a. If subject does not enter PTA phase then use week 52 visit date from SV domain b. If subject enters PTA phase then 
 i. Subject enters PTA on week 52 visit date then use a day prior to week 52 visit date ii. Subject enters PTA phase after week 52 then use week 52 visit date 2. Subject completes 52 weeks on core phase but discontinues switched treatment early i.e. core phase trt disposition reason is not equal to "COMPLETED" on DS domain 
 a. If subject does not enter PTA phase 
 i. if week 52 visit date $>$ treatment end date plus 27/1 day then use treatment end date plus 27/1 day ii. if week 52 visit date \leq treatment end date plus 27/1 day then use week 52 visit date b. If subject enters PTA phase 
 i. if week 52 visit date $>$ treatment end date plus 27/1 day then use treatment end date plus 27/1 day ii. if week 52 visit date \leq treatment end date plus 27/1 day then use a day prior to first dose in PTA phase 3. Subject does not complete 52 weeks on switched treatment i.e. core phase trt disposition reason is not

		equal to “COMPLETED” on DS domain and week 52 visit date is missing in SV domain then use min(treatment disposition date, treatment end date plus 1 day)
--	--	--

Note: DS: Disposition domain; SV:Visit domain; IAT: Initially assigned treatment

Monthly interval for efficacy endpoints (from ediary)

Monthly efficacy measurements will be calculated based on the subject's starting dose and visit schedule defined below using eDiary data collected from beginning of the baseline phase (week -4 visit) up to week 52 visit if subjects do not have safety follow up visit. For subjects with safety follow up, consider data up to the safety follow-up visit. The algorithm remains the same for initially assigned treatment and switched treatment. ediary data will be collected during core phase only and will not be collected during extension phase.

Table 2-3 Study intervals for efficacy endpoints – Erenumab and Oral prophylactics

Study phase	Assessment Time point	Interval based on dose dates	
		Start date	End date

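### SAP Table 2-2 leaves the initially assigned treatment safety period uncapped for subjects who switch, so a drug-free gap beyond the 27/1-day allowance is charged to the stopped drug

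*SAP*

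**What the plan says.** SAP Table 2-2 defines the IAT safety period in the core phase by four cases.

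- **Item 2**, early stop without a switch, week 52 visit attended: "if week 52 visit date > treatment end date plus 27/1 day then use treatment end date plus 27/1 day". If the week 52 visit falls inside the allowance, that visit closes the period. The exception is sub-case 2b(ii): for subjects who enter the extension, the period then runs to the day before the first extension dose.
- **Item 3**, early stop without a switch, no week 52 visit: "use min(trt disposition date, trt end date plus 27/1 day").
- **Item 4**, any switch: "Subject switches IAT then use day prior to date of first switch on DS domain". There is no reference to the last dose and no minimum.

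I read 27/1 as 27 days for erenumab and 1 day for orals. The table does not say so, but its erenumab-only extension row uses 27 alone.

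The switched period in the same table starts at "Date of first switch on DS domain", so the two periods touch and no interval is left for time between drugs. The SAP nevertheless expects such time: "There can be gap between end of first treatment and start of switched treatment" (section 1.1, Note). No maximum length is given.

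Exposure in SAP 5.6 ends elsewhere. For erenumab it is "computed as of last injection of study drug + 27 days - date of first injection of study drug +1"; for orals, "The duration of exposure for initially assigned treatment is computed as last dose date - First Dose Date + 1". SAP 2.8 presents safety by initially assigned treatment. SAP 2.8.1 adds a summary by switched treatment and exposure-adjusted incidence rates, without naming the denominator of those rates.

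**The concern.** Two subjects stop the same oral on the same day. One never starts another drug, and the IAT period closes a day later. The other starts a new oral some weeks afterwards, and every drug-free day in between is IAT time. The only difference is what happened later, yet an adverse event on the same date is attributed differently.

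The allowance also differs by arm, so the same gap produces different amounts of misattributed time under erenumab and under an oral. The documents suggest that switching will be commoner on orals: Protocol 1.1 cites one-year persistence of 13-16% for oral prophylactics in a chronic migraine claims analysis and 75-80% one-year retention for erenumab. What is at stake is the attribution of adverse events between assigned and switched treatment and, depending on the denominator, the exposure-adjusted rates.

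**Working it through.** The plan gives no figure for this point, so there is none to reproduce. The check applies the date rules.

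**Inputs.** L is the day of the last IAT dose, counted from first dose on day 1. S is the day of first switch, taken as the first dose of the new drug. Gap = S − L. The documents give no gap lengths; L = 85 and gaps of 1 to 84 days are my assumptions.

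**Formulas.**
- Item 4 end = S − 1.
- End under the non-switcher allowance = min(S − 1, L + 27) for erenumab, min(S − 1, L + 1) for oral.
- Excess = max(0, gap − 28) for erenumab, max(0, gap − 2) for oral.
- Exposure under SAP 5.6 = 85 + 27 − 1 + 1 = 112 days for erenumab, 85 − 1 + 1 = 85 days for oral.

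| Gap | Item 4 end | Erenumab: capped end | Excess | Item 4 minus exposure | Oral: capped end | Excess | Item 4 minus exposure |
|---|---|---|---|---|---|---|---|
| 1 | 85 | 85 | 0 | −27 | 85 | 0 | 0 |
| 14 | 98 | 98 | 0 | −14 | 86 | 12 | 13 |
| 28 | 112 | 112 | 0 | 0 | 86 | 26 | 27 |
| 29 | 113 | 112 | 1 | 1 | 86 | 27 | 28 |
| 42 | 126 | 112 | 14 | 14 | 86 | 40 | 41 |
| 56 | 140 | 112 | 28 | 28 | 86 | 54 | 55 |
| 84 | 168 | 112 | 56 | 56 | 86 | 82 | 83 |

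The excess begins at a gap of 3 days for an oral and 29 days for erenumab. At a gap of 28 days, one visit interval, it is 0 days for erenumab and 26 for an oral.

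The negative entries are the reverse mismatch. An erenumab subject who switches within 27 days of the last injection has an IAT period shorter than the section 5.6 exposure.

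**Rates, only if section 5.6 exposure is the denominator.** For one oral subject, ignoring the one-day allowance, the drug-free share is gap/(on + gap). If the event rate is the same off drug, the inflation is gap/on.
- 12 weeks on, 4 off: 4/16 = 25%; 4/12 = 33%.
- 12 on, 8 off: 8/20 = 40%; 8/12 = 67%.
- 24 on, 4 off: 4/28 = 14%; 4/24 = 17%.

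These are per-subject upper bounds. Across an arm they are diluted by subjects who do not switch. Suppose a fraction p switches after 12 weeks with a 4-week gap and the rest have 52 weeks of exposure. Inflation is then 4p/(12p + 52(1 − p)).
- p = 0.3: 1.2/(3.6 + 36.4) = 3.0%.
- p = 0.6: 2.4/(7.2 + 20.8) = 8.6%.

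Both values of p are assumed, and the result is again an upper figure. The planned rates are subject incidence rates, so a subject already counted for a term adds nothing in the gap.

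**The case against.** A reader might infer that the exposure-adjusted rates are inflated by a third or two thirds and that the between-arm safety comparison is therefore biased against orals. The documents do not support that. SAP 2.8.1 does not say that the denominator is the section 5.6 exposure, nor which Table 2-2 period the rates cover. The percentages describe single subjects with assumed gaps. In the erenumab arm, an early switch pushes the mismatch the other way.

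The date of first switch is also undefined. If it is the decision date, some or all of the gap falls in the switched period instead. Switching is reviewed at each 4-weekly visit and Protocol 6.2.2 permits cross-titration, so some switches will have no gap, or an overlap. Both points stand and limit what can be claimed about size.

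A further defence is that Protocol 12.5.2 runs the on-treatment period to 112 days after the last administration of any study treatment, under which gaps of 4 or 8 weeks count as on treatment. That is a real conflict with Table 2-2, but it does not rescue item 4. The 112-day rule does not say which of two drugs owns a gap, and items 2 and 3 already depart from it.

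Finally, touching periods guarantee that every event falls in one column or the other. That is a genuine advantage, and a cap must not push events out of the tables.

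**Conclusion.** The inconsistency holds on the face of Table 2-2: apart from sub-case 2b(ii), early stoppers who do not switch are capped and switchers are not. If the switch date is the first dose of the new drug, gap days beyond 28 (erenumab) or 2 (oral) are attributed to the stopped drug, so the same gap is treated unequally between arms. The section 5.6 mismatch is conditional on that exposure being the rate denominator, and it can run in either direction.

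The number of switchers, their gap lengths and hence the arm-level effect cannot be derived from the documents. The matter is confined to safety attribution: under SAP 2.5.1 a switcher has not completed a year on the assigned treatment and is a non-responder whichever end date is used. It should be corrected because the rule is ambiguous and easily repaired, not because a large bias has been shown.

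**What to change.** 1. Change item 4 to the minimum of the day before the first switch and the last IAT dose date plus 27/1 day, and state that 27 applies to erenumab and 1 to orals. Take the last IAT dose from dosing records: SAP 1.1 says that the treatment disposition form covers the last drug taken, which for a switcher is not the IAT.
2. Define the date of first switch as the first dose of the new drug.
3. Tabulate events between the capped end and the first switch in a separate off-treatment column by assigned arm, as well as listing them.
4. State the denominator of the exposure-adjusted rates and use the same period end for numerator and denominator. This also removes the reverse mismatch for early erenumab switches.
5. Reconcile Table 2-2 with the 112-day period in Protocol 12.5.2, and record the difference in SAP section 4, which currently reports no change.

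The cost is a few lines of SAP text, one changed derivation and one extra table column. No new data are needed, because section 5.6 already requires the dosing dates. The small downside is that gap events leave the IAT column, so readers must look at the added column to see all core-phase events.
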